*** Note: This section of the protocol will continue to be updated as the STVHCS OSI develops further.**

UPDATE (August 2015): In March 2015, [name] (Interim Under Secretary for Health, Veterans Health Administration) testified before the Committee on Veteran's Affairs in the United States Senate. She described the progress of the Opioid Safety Initiative in the VA (a transcript of her testimony can be found at: <http://www.veterans.senate.gov/imo/media/doc/VA%20Clancy%20Testimony%203.26.20151.pdf>). In her testimony, [name] described a system-wide decrease in opioid medication use throughout the VA (13%) and a decrease in persistent opioid use (15%). She noted that rescheduling of hydrocodone prescription has further curtailed how opioid medications are dispensed in the VA. Finally, she reported on the significance of CAM programs for pain management as part of the OSI. [name] report highlights a unique opportunity for this NIH-funded study to add to this effort. The PI has been working the VA Co-PI ([name]) to identify how the STVHCS PRC is managing OSI referrals and the PI will be working with the San Antonio OSI to establish this study as an OSI referral option (if approved by the NCCIH). This would not only vastly increase the feasibility of recruitment, but also allow for a comparison between referred and non-referred patients to add in programmatic decision making at a Federal level (regarding a program like FORT-A as a CAM referral option for OSI patients). There is no better time to do this, and addition of OSI-referred patients to our inclusion criteria would make this possible.

5.4 Adherence Assessment

Adherence for this research is addressed in the following three ways:

Adherence of interventionists and assessors to manualized assessment and treatment procedures. All interventions (FORT-A group, biofeedback, individual psychotherapy) will be provided by one of the licensed Psychologist study investigators (or supervised STRONG STAR postdoctoral fellows/interns) and a licensed Physical Therapist. Psychologists will be trained in the group intervention by the PI and then certified by [name] using a “see one, do one” approach in which they will observe the [name] running all 12 sessions of a clinical (non-research) group and be observed by her to obtain certification. During her observation, [name] will use a checklist of group session content (adapted from the same checklist used in the original FORT trial) to ensure that at least 90% of required content is covered at each session. If successful (e.g., covers 90% of each session), the Psychologist will be “certified” and will be eligible to teach others. The PI will also train interventionists in biofeedback using the certification process he developed for the U.S. Air Force’s biofeedback lab at Lackland Air Force Base (e.g., complete two mock biofeedback sessions with the PI before seeing FORT-A patients). Group psychotherapy and biofeedback will be supervised weekly by [name] (the PI will be available to address technical questions about the group treatment and biofeedback, but will do this outside of supervision (in order to maintain blinding). Independent evaluators (IE’s) will be trained on all psychosocial assessments by the PI and [name]. The IE’s will be trained on the timeline followback (TLFB) opioid assessment method by [name], who will train each IE through 2 role play cases and record two clinical TLFB assessments for review. If the IE achieves a 90% success rate or better both times they will be certified for TLFB. If they have been certified in TLFB for another study, then this step can be skipped. We will randomly audiotape subsequent psychosocial assessment, TLFB, and FORT-A group administrations ($\approx 10\%$) to assess for drift from the protocol using standardized checklists of required content to cover and ignore in each session (performed by a non-study RA). The Physical Therapy assessment and treatment programs will be manualized and videotaped for protocol fidelity (accepted if at least 90% of required content is covered). PT’s and/or PT students will be trained by [name], who will also supervise. A random selection ($\approx 10\%$) of videotapes will be reviewed by a non-study RA to ensure there is no drift from the protocol. Prolonged Exposure (PE) treatment for PTSD (implemented during individual FORT-A individual psychotherapy appointments) will be supervised by [name] who is trained in PE.

Maintaining the blind during assessment certification: As is the case in other STRONG STAR studies, IEs will be trained and certified in assessment using non-study (i.e., clinical) cases. This will allow for a more open dialogue about the assessment process during training with Drs. [name], [name], and [name]. Fidelity to the intervention will be completed by a STRONG STAR Research Assistant who is not part of this study team using standardized checklists.

Participant adherence to FORT-A treatment. As described above, FORT-A is an

intensive, multi-component program. In order to be adherent to treatment, each participant will need to attend group sessions, individual psychotherapy session, biofeedback sessions, and Physical Therapy sessions. One benefit of incorporating all of these programs into a consolidated, intensive program is an increased likelihood that participants will attend all components. In fact, in the original FORT trial, every FORT participant attended all FORT classes and all PT sessions (with the exception of one who elected to undergo shoulder surgery during his enrollment in the study and ended his participation early). FORT-A classes and PT session have some serial dependency (i.e., individual sessions build on one another), but many can stand alone. FORT-A classes include homework, generally in the form of skills practice. Individual FORT-A psychotherapy includes a 6-session Prolonged Exposure protocol for PTSD symptoms. Prolonged Exposure requires “trauma rehearsal” to promote habituation to traumatic memories. PT for FORT includes group exercise 4 days a week followed home-based exercise on the weekends guided by “flowsheets.” All interventionists will be trained in motivational interviewing and problem-solving skills to help maximize patient adherence to study tasks. For this research, “adherence” for each FORT-A component will be defined as follows:

FORT-A Component	Adherence Criterion	Adherence Management
FORT-A Psychotherapy Group (4 days/wk x 3 wks)	10/12 Classes	Make-up missed class in extra individual session
FORT-A Physical Therapy Group (4 days/wk x 3 wks)	10/12 Sessions	Make-up missed PT with +1 flowsheet
Individual Psychotherapy (2 days/wk x 3 wks)	5/6 Sessions	Reschedule missed IP session
Biofeedback (4 days/wk x 3 wks)	2/6 Sessions	Reschedule missed BFB session
Homework: Group Individual Psychotherapy PT	8/10 practice sessions 4/5 trauma rehearsals 2/2 weekend flowsheets	Give opportunity for practice/trauma rehearsal before class

Study interventionists will maintain study activity logs (see **Appendix E**, maintained centrally by the Study Coordinator) where they will log the date and completion status of each clinical activity (including sessions attended or missed). These will be brought to weekly interdisciplinary staffing meetings where adherence will be discussed and problem-solved by the interdisciplinary treatment. The PI will attend parts of these meetings to monitor study progress and troubleshoot general problems (he cannot stay when specific patients are discussed, even by study ID, because he

would become aware of which IDs are in the FORT-A group). A study activity log example is below:

FORT-A; Week 1				
ID	Date	Activities	Attended?	Notes
10EX1	01/01/2001	Group PT IP	Y Y Y	Patient reported an injury on 01/02/2001; entered in AE log as non-study-related; consulted study MD on 01/05/2001; pt was cleared to continue
	01/02/2001	Group PT BFB	Y Y Y	
	01/03/2001	---- Rest Day ----		
	01/04/2001	Group PT IP	Y N Y	Patient given an extra flowsheet for the evening of 01/05/2001 to make up that missed session; BFB missed on 01/05/2001 and was rescheduled for next week
	01/05/2001	Group PT BFB	Y N N	

Participant adherence to assessments. Adherence to assessments is vital to this work. For this research, assessment is broken into 3 distinct categories (psychosocial, functional, opioid). Most assessments are administered at pre-treatment, post-treatment, 6-month follow-up, and 12-month follow-up. A few measures are ongoing. Adherence to assessment is defined as completion of assessments within a specified window of time. Categories of assessment, assessment windows, and managing adherence to assessments are as follows:

FORT-A Assessment Category	Assessment Window	Tips to Promote Adherence
Psychosocial Assessments	Pre-treatment/Baseline * ≤ 2 weeks before treatment	Schedule pre- and post-tx assessment with first and last days of tx
Functional Capacity Assessments	Post-treatment * ≤ 2 weeks after Tx completed	
Opioid Assessments	6-month follow-up *24 weeks (± 2 weeks) after Tx completed	Reminder/check in phone calls every month
	12-month follow-up *50 weeks ± 2 weeks after Tx completed	Psychosocial and FCE scheduled on same day

Ongoing Assessments	MEMS/Actiwatch – Start at pre-treatment and end at 12-month f/u TLFB/MQS – Administered at pre- and post-treatment and every month after post-treatment.	
----------------------------	---	--

Study evaluators will maintain active logs for assessments identifying participants by unique ID # only and including date of evaluation, whether or not evaluation was in a study window, if PI approved out of window assessment (when outside of a window), whether an AE was identified in the assessment (e.g., suicidal ideation on the PHQ-9 item #9), and notes about assessment (see **Appendix F**). These logs will be monitored by the PI and coordinator weekly to ensure that assessments are completed on time. An example assessment log is as follows:

ID	Assessment	Assessment Domains	Assessment Date	Window? (Approved?)	Notes
10EX1	Pre-Treatment * within 2 wks before tx phase	Psychosocial	01/01/2001	Y	Treatment Phase Start 01/04/2001 End 01/25/2001 10EX1 forgot MEMS and Actiwatch at Post-Tx; PI approved out of window download; we can use data up to 01/25/2001 10EX1 sustained injury playing basketball on 07/20/2001; not cleared for FCE for 3 months; PI denied out of window assessment due to injury delay 10EX1 completed FCE on 01/24/2002 but not time for testing; r/s for when returns from vacation (01/24); PI approved out of window
		FCE	01/01/2001	Y	
		TLFB	01/01/2001	Y	
		MEMS	01/01/2001	Y	
		Actiwatch	01/01/2001	Y	
	Post-Treatment * within 2 wks after tx completed	Psychosocial	01/25/2001	Y	
		FCE	01/25/2001	Y	
		TLFB	01/25/2001	Y	
		MEMS	02/10/2001	N (Y)	
		Actiwatch	02/10/2001	N (Y)	
	6-Month *24 weeks ± 2 weeks after tx completed	Psychosocial	07/22/2001	Y	
		FCE	---	N (N)	
		TLFB	07/22/2001	Y	
		MEMS	07/22/2001	Y	
		Actiwatch	07/22/2001	Y	
	12-Month *50 weeks ± 2 weeks after tx completed	Psychosocial	02/07/2002	N (Y)	
FCE		01/24/2002	Y		
TLFB		02/07/2002	N (Y)		
MEMS		01/24/2002	Y		
Actiwatch		01/24/2002	Y		

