3. STUDY DESIGN

To address the primary and secondary hypotheses, this research study was designed as a randomized clinical trial comparing the manualized FORT-A treatment to treatment as usual for polytraumatic chronic musculoskeletal pain in the STVHCS Polytrauma Rehabilitation Center. Eligible OEF/OIF/OND Veterans will be randomized to either arm in 1:1 random permuted block randomization with no stratification. Because the FORT-A is a group intervention, it is vital that we randomize into meaningful blocks of at least three Veterans and no more than seven. Three is chosen as the lower block boundary because the PI had success in the original FORT trial with FORT groups of three active duty service members. Seven Veterans will be the upper boundary because FORT groups of more than seven military members were difficult to manage. In block randomization with static boundaries, study staff overseeing randomization will lose blinding if they are aware of how many participants have already been randomized into each block. For example, if block boundaries are always 5 participants and the treatment as usual condition has 5 participants while the active treatment has 4, then the staff randomizing the 10th participant will know with certainty that this participant will be in the active treatment group. To protect blinding, we have chosen to implement a variable boundary randomization for which the study staff randomizing patients will be blind to the boundaries and the resulting condition of the participant (see Sanghaei, 2011). The PI, Independent Evaluators, and Biostatistician will be blind to the condition of all participants until data lock. A research assistant overseeing randomization will also be blinded by randomizing unique patient identifiers into variable permuted blocks (through the STRONG STAR Data Core) by unique study identifier (e.g., first participant identified as #0001). All assessments given by Independent Evaluators will be labeled with just the unique identifier. Only the study coordinator (and co-coordinator) will be able to link unique identifiers to individual participants.

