responded best to group PT on Monday, Tuesday, Thursday, and Friday with a break on Wednesday to allow for recovery. The PRC PT Service has already agreed to allow the study to use their space and equipment for study-related PT. PT providers will be encouraged to participate in FORT-A group psychotherapy sessions and STRONG STAR Interns/Fellows will be encouraged to sit in on group PT sessions (to maintain continuity in this interdisciplinary program).

Blinding: [name] or a PRC PT/OT will monitor adherence to recommended PT practice and will not share details of the PT with the PI or any other blinded research personnel.

Providers and Qualifications: PT will be provided by [name], her Physical Therapy students with WOC appointments at the VA, or existing PRC PT/OT providers. The number of students PT interventionists over time will vary and is indeterminate but will be greater than 2. Skills required for the PT portion of the treatment will include skills for rehabilitation of chronic pain, strength and conditioning, and improved range of motion for the back and extremities.

Interdisciplinary Staff Meetings (Manual Under Development)

The entire study team (with the exception of IEs) will meet weekly to discuss progress of FORT-A participants and PRC participants. Participants will be discussed without identifiers (even using the unique identifier would unblind the PI to the condition of the participant. These meetings will be run by the research coordinator and/or co-coordinator who will be aware of patient identity in case an adverse event is noted and needs to be addressed. Issues discussed in these weekly meetings include adherence to protocol, treatment goals, problems with treatment, and changes in medication or medical status. These meetings will occur from 1200-1300 in the PRC with the VA PI's ([name], [name]) in attendance.

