6.2.3.1 Maintaining Blinds

During treatment sessions, interventionists are asked not to refer to the participant by name and all quality assurance audio files are labeled only with the date of intervention, the session number, and the unique study identifier for the participant(s) involved. Because it is possible that the Research Assistant (RA) completing quality assurance may become aware of the identities of participants in the individual or group treatments, RA's who complete quality assurance will not take part in outcomes assessments (which will only be completed by Independent Evaluators through STRONG STAR).

Independent Evaluators will enter participant data from assessments directly into the secure STRONG STAR SQL Database using standard STRONG STAR operating procedures (see STRONG STAR Data Entry SOP, Appendix I).

** The PI and study physicians ([name], [name]) will sit in on weekly interdisciplinary staff meetings with study interventionists to discuss the progress of all study participants (both FORT-A and Treatment-As-Usual) during which participants will be discussed by case number only.

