7.1 Specification of Safety Parameters

Section 7.3 of this protocol describes a number of formal assessment measures and related safety thresholds. Along with these formal assessment measures, we will also assess pain intensity ratings for each participant before and after each session of study-related Physical Therapy. The PI published a study of pain intensity ratings in functional restoration programs and noted that participants who reported pain on a 0-10 Numeric Rating Scale between 8-10/10 generally demonstrated worse outcomes after treatment. Thus, individuals reporting pain after PT sessions with pain ratings between 8-10/10 will be assessed for safety by [name] or a PRC PT/OT and discussed with the PI (using unique identification number).

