Pain Intensity	Numeric Rating Scale (NRS)	Assessed at every assessment interval and at every physical therapy appointment for FORT-A participants Opinions vary on a clinically meaningful change in pain numeric rating, but many agree that an increase in pain rating > 2 points is clinically significant (see [name] et al., 2006)
Emotional Distress	PHQ-9	Given at every assessment interval and once a week during group treatment

		
sessions for FORT-A participants
 
Change in PHQ-9 scores is clinically significant if the total score rises above 15 (as defined in Kroenke & Spitzer, 2002). Those who begin the study with a score above 15 show significant change (requiring AE report) if the score rises 5 points or more. If item #9 increases at all, this will be reported an AE. An increase of Item #9 by 2 points or more will be considered a SAE.

Opiate Withdrawal	SOWS	
The Subjective Opiate Withdrawal Scale will be given to all FORT-A participants once a week during treatment and at all assessment intervals for all follow-up intervals. A SOWS score of 11 or more will indicate an AE requiring follow-up (based on established cut-off scores).

This study maintains a weekly research meeting (starting September 2015; currently set for Thursday morning from 1030-1100 at the STRONG STAR Conference Room with an open phone line for those who need to call into the meeting) to discuss research progress and to discuss participant status and flow throughout the research process. All Adverse Events (AEs) and Serious Adverse (SAEs) will be discussed at these meetings (attended by all study staff). To protect blinding, participants will be discussed by unique identifier only.

AE reporting procedures (as described in the attached SOP) will begin immediately after an AE is noticed and will be reported to the IRB after discussion at the weekly research meeting. SAEs must be reported to the IRB within 24-48 hours. If a protocol deviation, SAE or UPIRSO is not reported within 48 hours, a reason will need to be documented on the P50 form.

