7.5 Followup for Adverse Events

If an adverse event does not require disenrollment and referral to VA physical or mental health services, then the research team will offer adjunctive services for attrition prevention as outlined in the STRONG STAR ASAP SOP (**Appendix O**). Adjunct services and attrition prevention (ASAP) involves the structured provision of extra adjunctive psychotherapy or medical consultation services designed to mitigate risk of adverse events and maintain participants on protocol (within the limits of good ethics and clinical practice). ASAP sessions can be prompted by the participant, an IE, or an interventionist. These sessions are defined in the SOP as “any out of protocol contact (in person or by telephone) lasting longer than 20 minutes. Each participant is allowed three ASAP sessions during protocol intervention. If more intervention is needed, or the PI believes that a higher level of intervention is needed, then the participant will be dropped from protocol treatment and referred for appropriate intervention in the VA. For participants remaining on protocol with ASAP or referral services, progress will be briefed to the PI daily to monitor progress. When the participant and provider report resolution or stability of symptoms, the participant will be re-assessed with the index measure (e.g., PHQ-9 for depression, NRS for pain) and the results will be discussed with the PI (using only the unique identifier for the participant to maintain blinding) for a final determination of resolution and continuation on protocol.

Please note that STRONG STAR maintains a separate SOP for the monitoring, management, and intervention of suicide risk in study participants (as detailed in **Appendix P**). As detailed in the Suicide Risk SOP, all study staff are thoroughly trained in suicide risk assessment, with formal assessments overseen by a licensed psychologist. This SOP describes specific algorithms for risk level determination and pathways for intervention, follow-up, and implications for research involvement.

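### The plan says the study ID alone would unblind the PI, yet Section 7.1 reports FORT-A physical therapy alerts to him by that ID, and he helps adjudicate outcomes filed under it

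*Combined protocol and SAP*

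**What the plan says.** Section 3 sets the aim: "The PI, Independent Evaluators, and Biostatistician will be blind to the condition of all participants until data lock". Two later sections say what would defeat it. On the weekly interdisciplinary meetings, Section 5.2 warns that "even using the unique identifier would unblind the PI to the condition of the participant". Section 5.4 says of the PI that "he cannot stay when specific patients are discussed, even by study ID", and gives the reason: he would find out which IDs are in FORT-A.

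The safety sections treat that identifier as the protection. Section 7.1 plans to "assess pain intensity ratings for each participant before and after each session of study-related Physical Therapy", and ratings of 8-10 out of 10 after a session are to be "discussed with the PI (using unique identification number". The Section 7.3 monitoring table describes the pain rating as "Assessed at every assessment interval and at every physical therapy appointment for FORT-A participants". For adverse events being followed to resolution, Section 7.5 says "the results will be discussed with the PI (using only the unique identifier for the participant to maintain blinding". Section 6.2.3.1 has the PI sit in on the staff meetings, "during which participants will be discussed by case number only".

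Sections 5.4, 9.5.1 and 9.5.2 give the PI case-level roles in outcome data: monitoring assessment logs, approving or denying out-of-window assessments, and sitting with others to adjudicate unclear ODI items, physical measures and medication data.

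**The concern.** The plan holds two incompatible views of the study ID. In Sections 5.2 and 5.4 it is enough to reveal arm to the PI. In Sections 7.1, 7.3, 7.5 and 10.2 it is the means of keeping him blind. Both cannot be right when the report comes from an activity that exists in one arm only.

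The PI is also not a bystander to the outcome data. If he knows that an ID is FORT-A and later meets the same ID in an adjudication or a window request, his decision on whether a value is accepted, how it is scored, or whether a late visit counts is made with knowledge of arm. A trial report that the PI was blind until data lock could not be supported from this plan.

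**Working it through.** No arithmetic applies beyond a bound, and the plan states no figure to reproduce. The check is to set the sections side by side.

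**Step 1. Does the Section 7.1 route reveal arm?**
- The trigger is a rating after study-related physical therapy (7.1).
- The rating at physical therapy appointments is specified for FORT-A participants (7.3).
- The research gives treatment-as-usual participants no further physical therapy recommendation (5.1.1). They may attend such therapy again, but not as a study session.
- The identifier used is the unique ID (7.1).

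So an ID that reaches the PI by this route belongs to FORT-A.

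**Step 2. Do other safety routes reveal arm?**
- During treatment, the PCL-5 at each individual PTSD session, the weekly PHQ-9 and the weekly SOWS are specified for FORT-A participants (7.3). Adverse events are discussed by unique ID at a weekly meeting of all study staff (7.3), and are brought to the PI by unique ID (10.2). That meeting covers both arms, so an ID raised there reveals arm only when the event is traceable to a FORT-A session or measure.
- Resolution decisions under 7.5 go to the PI by unique ID. These may reveal arm. Section 8 describes the adjunctive (ASAP) sessions as being with the participant's individual or group psychotherapist, which points toward FORT-A but does not settle it.

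**Step 3. Staff meetings.** Section 5.4 has the PI leave when specific patients are discussed. Section 6.2.3.1 has him sit in, with case numbers. Section 5.2 proposes meeting-only identifiers, separate from the research ID and linked by the Coordinator. These would help, but they cover staff meetings only, and the same paragraph doubts that they can be implemented.

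**Step 4. What does he decide under the same ID?**

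| Decision | Section | Identifier stated |
|---|---|---|
| Blank or unclear ODI items | 9.5.1 | Unique ID |
| Functional capacity and Actiwatch data | 9.5.2 | Unique ID |
| Medication data (TLFB, MQS, MEMS) | 9.5.2 | None for TLFB; de-identified for MEMS |
| Out-of-window assessments | 5.4 | Unique ID |

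The sample logs in 5.4 confirm the link: the ID 10EX1 appears in both the FORT-A activity log and the assessment log. In the sample assessment log the PI denies one out-of-window functional capacity evaluation, which leaves the 6-month value missing, and approves other late assessments.

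**Step 5. Size.** Planned FORT-A participants: 130 / 2 = 65. The documents give no rate of 8-10 ratings, of adverse events from FORT-A sessions, or of adjudications. The number of IDs revealed therefore lies between 0 and 65 and cannot be narrowed.

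**The case against.** The strongest reply is that the harm is small and partly guarded against.

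- **Rare use, and a self-reported endpoint.** Section 9.5.1 expects ODI adjudication almost never, and shares it with the evaluator and the Coordinator. The ODI is completed by participants who cannot be masked (9.2). The leak set out here runs to the PI, not to the evaluators' own ratings or the biostatistician. This stands, and it limits the consequence for the primary result.
- **Meeting identifiers.** The case number in 6.2.3.1 may be the separate identifier of 5.2. If so, 6.2.3.1 and 5.4 differ on whether the PI stays, but disclosure by outcome ID is not shown. This also stands. It does not reach 7.1, 7.3 or 7.5, which use the unique ID.
- **Adjunctive sessions.** A reader might infer that every ASAP contact tells the PI the participant is in FORT-A. The documents do not support this. In 7.5 the daily briefing names no identifier; the unique ID belongs to the later discussion of re-assessment results. Sessions may be prompted by the participant or an evaluator, may include medical consultation, and the briefing also covers participants on referral services.
- **Opioid interview.** A reader might also infer that TLFB problems reach the PI by unique ID. Section 9.5.2 does not say so. The general rule in 10.1 that records are entered under the unique ID makes it plausible, but no more.
- **Unseen material.** The adverse event and ASAP procedures (Appendices J, M and O) and Figure 2 cannot be seen here and may add detail. They would not remove the conflict between 7.1 and 5.4 in the protocol text.

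**Conclusion.** The contradiction is real and rests on the current text alone. By the plan's own reasoning in 5.2 and 5.4, the Section 7.1 alerts reveal FORT-A membership to the PI, and he holds case-level roles in outcome data under the same ID. Other adverse event reports and resolution decisions may also reveal arm, depending on their source. The stated PI blinding is not a property this design reliably has.

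A reader might go further and conclude that the primary comparison is materially biased. The documents do not support that: ODI adjudication is exceptional, and the score is self-reported. Functional capacity, TLFB and window decisions leave more room for judgement and are more exposed. The TLFB part assumes that the PI can recognise the participant, which 9.5.2 does not state. The number revealed is 0 to 65; any narrower figure would be a guess.

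This should be corrected, at modest priority. It concerns who receives and decides what; it takes no position on the safety thresholds or on any participant's care.

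**What to change.** Reconcile 6.2.3.1, 7.1, 7.3 and 7.5 with 5.2 and 5.4, in one of two ways.

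**Preferred.** Leave the safety duties with the PI. State in Section 3 and Figure 2 that he is not reliably blind to condition. Remove him from outcome adjudication (9.5.1, 9.5.2) and from out-of-window approval (5.4), and give these to existing team members who are blind to condition. The Coordinator, who knows condition under 6.2.3, should not be the replacement. Whoever takes over should not hear FORT-A session events by unique ID at the weekly meeting in 7.3.

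**Alternative.** Keep the PI blind. Route alerts from FORT-A sessions to the supervisors who are already unblinded under 6.2.3. Reassign the matching case-level decisions on adverse event severity, relatedness, resolution and retention in 7.4, 7.5 and Section 8, since the PI cannot make these without case details. Before using the study physicians for this, confirm their blinding status and their part in the prescription-monitoring data (9.5.2), so that the leak does not move to people handling opioid data.

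Under either option, settle whether the PI stays in the staff meetings and whether the separate meeting identifiers are adopted.

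The cost is revised wording, some reassignment of duties and, under the preferred option, a less favourable blinding statement. Sample size and analysis do not change.
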